### 6.2.2.2 Time to pain progression

Time to pain progression (PP) is defined as time from randomization to pain progression, where progression is defined as an increase of 2 or more points from baseline in question 3 of the Brief Pain Inventory-Short Form questionnaire (BPI-SF) related to the worst pain in the last 24 hours taken as a 7-day average for post-baseline scores, or initiation of short or long-acting opioids for pain, whichever comes first. Initiation or change in the use of other non-opioid analgesics is not used in the analysis of pain progression.

List of opioids for cancer pain is available in Appendix 9.10.

Questionnaire BPI-SF is detailed in Appendix 9.2.

A minimum number of 4 completed daily reports at each reporting time point out of the 7 days required per protocol are needed to consider valid the assessment.

If the complete date of the assessment is not known, but the year and month are available, day 15 of the month will be used for the calculation.

Table 10 will be used for calculating the time to first pain progression. Time to Pain progression = End Date – Date of Randomization +1.

**Table 10: Censoring Rules for Pain Progression**

Situation	End Date on or prior to cut-off date	Censored
Recorded pain progression during the study	Date of the first assessment that qualified as pain progression	No
No baseline BPI-SF assessments	Date of randomization	Yes
Discontinued the study before the post-baseline BPI-SF assessments	Date of randomization	Yes
Death during the study before pain progression	Date of last visit the patient was known not to have progressed or randomization date whatever comes later	Yes
Patient has no recorded pain progression at data cut-off	Date of last visit the patient was known not to have progressed or randomization date whatever comes later	Yes
Patient lost to follow-up before data cut-off	Date of last visit the patient was known not to have progressed or randomization date whichever comes later	Yes
Patient taking opioids for any reason	Date of randomization	Yes

within 4 weeks prior to randomization		
---------------------------------------	--	--

This endpoint is selected from the ADTTE dataset using variable PARAMCD equal to ‘PP’.

A log rank test stratified by stratification factor of PSADT ( $\leq 6$  vs.  $>6$  months) and use of osteoclast-targeted therapy (yes vs. no) at randomization will be used to compare the darolutamide treated and placebo groups.

The hazard ratio as well as its 95% CI will be presented based on fitting a Cox regression model with treatment as factor and stratified by PSADT ( $\leq 6$  vs.  $>6$  months) and use of osteoclast-targeted therapy (yes vs. no) at randomization.

Kaplan-Meier survival curves (product-limit estimates) will be presented by treatment arm. The Kaplan-Meier estimate of the median survival time and first and third quartiles will be presented with 95% CI. Greenwood's formula will be used for the standard error of the Kaplan-Meier estimate in the calculation of these confidence limits.

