6.3.2.4 Time to pain progression

Pain progression is defined as an increase of ≥ 2 points from baseline (day 1 score) in question 3 of BPI-SF (related to the worst pain in the last 24 hours) taken as a 7-day average, or initiation of short or long-acting opioids for pain, whichever comes first.

Pain will be assessed with the BPI-SF questionnaire (Appendix 4) during the visit, pain diary entries from 6 days preceding the visit and opioid use from baseline until documented pain progression. The pain diary consists of 6 copies of BPI-SF questionnaire.

Initiation or change in the use of other non-opioid analgesics is not used in the analysis of pain progression.

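### SAP Table 10 both counts and censors an opioid start when the baseline BPI-SF is missing, or when the patient left the study before a post-baseline one, and gives no order of precedence

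*SAP*

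**What the plan says.** SAP 6.2.2.2 counts pain progression when the BPI-SF worst-pain item rises by 2 or more points, "or initiation of short or long-acting opioids for pain, whichever comes first". An opioid start is therefore an event by itself. Protocol 6.3.2.4 has the same composite and includes "opioid use from baseline until documented pain progression" in the data collected. Protocol 5.7.1 has concomitant treatments recorded from consent to the end-of-study treatment visit. An opioid start can thus be known when no questionnaire exists.

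Four rows of SAP Table 10 matter here:

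- Row 1, "Recorded pain progression during the study": an event, dated "Date of the first assessment that qualified as pain progression".
- Row 2, "No baseline BPI-SF assessments": censored at randomisation.
- Row 3, "Discontinued the study before the post-baseline BPI-SF assessments": censored at randomisation.
- Last row, opioids taken in the 4 weeks before randomisation: censored at randomisation.

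The time formula ends in "Date of Randomization +1", so censoring at randomisation gives a time of one day. Rows 2 and 3 do not mention opioids. No order of precedence is stated, and 6.2.2.2 lists no sensitivity analysis.

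**The concern.** Rows 2 and 3 look only at the questionnaire, although half of the composite does not need it. Two programmers could follow Table 10 faithfully and give the same patient different outcomes.

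The endpoint is not a minor one. SAP 6.2.2 places it second in the hierarchy, after overall survival and ahead of chemotherapy and skeletal events, under an overall two-sided 0.05. Tables 7 and 8 reuse the interim dataset if it is tested at the final analysis, so later data would not replace the derivation made at the first analysis. Row 3 also depends on what happens after randomisation. A patient who starts an opioid and then leaves the study early may be leaving because of his disease, and censoring him on day 1 would not be independent of pain.

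**Working it through.** **1. The plan's own figures.** The documents give no event count, hazard ratio or power for pain progression. The only power figure is for MFS: 91% with 385 events. I used it to check the log-rank formula needed in step 5: power = Φ(√(d × 2/9) × |ln HR| − 1.96), where 2/9 = 2/3 × 1/3 for 2:1 allocation. SAP 3.1 assumes 5% with baseline metastasis: 0.05 × 1500 = 75 uninformative events, which leaves 385 − 75 = 310. The diluted hazard ratio is exp(ln 0.65 × 310/385) = 0.707, which rounds to the SAP's 0.71. Power is then 89.4% (88.7% with the rounded 0.71), close to the simulated 91%.

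**2. One patient, two outcomes.** Take a patient with no baseline BPI-SF and a recorded opioid start at time 60 days. Row 1 makes him an event at 60 days. Row 2 censors him at 1 day. Row 3 does the same to a patient who starts an opioid at 60 days and then leaves the study with no post-baseline BPI-SF.

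**3. Why changing the order alone is not enough.** Add patient B, who has no baseline BPI-SF and no opioid, and whose opioid use was last assessed at week 16 (time 16 × 7 + 1 = 113 days).

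| Rule | Opioid starter | Patient B | Events | Patient-days |
|---|---|---|---|---|
| Rows 2 and 3 win | censored, 1 | censored, 1 | 0 | 2 |
| Row 1 wins, nothing else changed | event, 60 | censored, 1 | 1 | 61 |
| Opioid start wins, others censored at last opioid assessment | event, 60 | censored, 113 | 1 | 173 |

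The first rule loses the event. The second keeps it but drops the event-free time of comparable patients, so inclusion depends on outcome. Only the third uses both.

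**4. How the SAP treats similar cases.** Table 2 (MFS) meets the same problem and settles it: a patient who leaves before any post-baseline scan is censored at randomisation, but is an event if he dies within 32 + 1 weeks. Table 19 (time to first opioid use) dates the event at first opioid use, with no questionnaire condition. Table 10 does neither.

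**5. Size (assumed inputs).** Events at stake = 1500 × share in rows 2 or 3 × proportion of those with an opioid start.

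- 1500 × 0.01 × 0.02 = 0.3
- 1500 × 0.03 × 0.10 = 4.5
- 1500 × 0.10 × 0.20 = 30

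If there were 300 pain-progression events and a hazard ratio of 0.70 (both assumed), power is Φ(√(300 × 2/9) × 0.3567 − 1.96) = 83.0%. It falls to 82.3% with 5 events lost, 81.7% with 10 and 78.9% with 30.

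**6. Effect on the hazard ratio (assumed inputs).** A small simulation put both orders on the same data: 1500 patients at 2:1, exponential times with a placebo median of 36 months, true hazard ratio 0.70 or 1, 12 repetitions per scenario. It compares row 1 winning with rows 2 and 3 winning.

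- Equal shares in both arms (3% or 5%): 0.721 against 0.718, and 0.729 against 0.731.
- 4% on placebo, 8% on darolutamide, 20% of them opioid starters: 0.736 against 0.710; with no true effect, 1.005 against 0.978.
- 8% on placebo, 4% on darolutamide, 20% starters: 0.678 against 0.688; with no true effect, 0.956 against 0.977.

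The two orders differ by 0.002 to 0.003 when the shares are equal, and by 0.010 to 0.027 when one arm has twice the share of the other. Twelve repetitions are too few for the levels themselves to be relied on.

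**The case against.** The best defence is that row 1 comes first, requires no questionnaire, and follows a definition that makes an opioid start an event. A sensible programmer would code the event. It is right that the SAP nowhere says an opioid starter is censored. A reader might infer that Table 10 definitely discards these events, but the documents show only an unresolved overlap.

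Reading the table from the top is not a safe solution, however. It would make row 1 override the last row too, so a patient on opioids just before randomisation would count as an event if he later progressed. It would also leave patient B in step 3 censored on day 1.

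A reader might also infer that every patient without a post-baseline BPI-SF is censored on day 1. Row 3 is narrower, because it requires study discontinuation. A patient who only stops treatment is due an end-of-study treatment visit at which the BPI-SF is collected (Protocol 6.1.2.6). Unless he starts a prohibited treatment before metastasis, Protocol Table 4 then provides for it every 16 weeks. Row 3 is left mainly with patients who withdraw completely or die before any such assessment.

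A general claim of bias goes too far as well. The baseline BPI-SF is completed on day 1 before dosing, under blinding, so row 2 should be roughly balanced between arms.

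The separate opioid endpoint in SAP 6.2.3.8 would reveal starts missing from pain progression, but its p-value is informative only and it does not correct the secondary endpoint. Finally, a patient without a baseline score can never meet the score component. That is a genuine cost of keeping him at risk.

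**Conclusion.** The point holds as a contradiction between the composite definition and two rows of its censoring table, on an alpha-controlled endpoint. Both available readings are flawed: one loses valid events, the other admits these patients only through their events. The effect is probably small. The range of 0.3 to 30 events rests wholly on assumed shares, as do the power and hazard-ratio figures, and the documents can neither confirm nor narrow them. Row 2 mainly costs events. Row 3 could bias the hazard ratio, but only if early study withdrawal differs between arms, on which the documents are silent. This is a low-priority correction that is worth making because it is cheap.

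**What to change.** Change Table 10 as follows:

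1. State that a recorded opioid initiation after randomisation is an event on the opioid start date and takes precedence over rows 2 and 3.
2. Restrict rows 2 and 3 to patients with no opioid start, and censor them at the last date opioid use was assessed, or at randomisation if there is none.
3. Leave the row for opioids in the 4 weeks before randomisation unchanged, and state that it takes precedence.
4. Run the day-1 censoring version as a sensitivity analysis, and report by arm how many patients fall in rows 2 and 3 and how many of them start an opioid.

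The cost is table wording and one further analysis, since the opioid data are already collected. The downside is that patients without a baseline BPI-SF contribute through the opioid component only, which the report should say.

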### 6.2.2.3 Time to initiation of first cytotoxic chemotherapy

The time to cytotoxic chemotherapy (CYTOC) is defined as time from randomization to the start of the first cytotoxic chemotherapy cycle. Patients who have not taken cytotoxic chemotherapy will be right censored at their last visit.

Cytotoxic chemotherapy drugs are defined with ATC code L01A, L01B, L01C, L01D and L01X. The list of all cytotoxic chemotherapy is available under Appendix 9.7.

If the complete date of the cytotoxic chemotherapy is not known, but the year and month are available, day 15 of the month will be used for the calculation.

Table 11 will be used for calculating the time to first cytotoxic chemotherapy. Time to cytotoxic chemotherapy = End Date – Date of Randomization +1.

**Table 11: Censoring Rules for Cytotoxic Chemotherapy**

Situation	End Date on or prior to cut-off date	Censored
Recorded cytotoxic chemotherapy during the study	Date of the first assessment that qualified as cytotoxic chemotherapy	No
Death during the study before cytotoxic chemotherapy	Date of last visit at which cytotoxic chemotherapy question was collected or randomization date whatever comes later	Yes
Patient has no recorded cytotoxic chemotherapy at data cut-off	Date of last visit at which cytotoxic chemotherapy question was collected or randomization date whatever comes later	Yes

Patient lost to follow-up before data cut-off	Date of last visit at which cytotoxic chemotherapy question was collected or randomization date whatever comes later	Yes
---	--	-----

Cytotoxic chemotherapy is a specific antineoplastic therapy and therefore the CRF question “Has the patient taken any new antineoplastic therapy since previous visit?” implies the question for cytotoxic chemotherapy.

This endpoint is selected from the ADTTE dataset using variable PARAMCD equal to ‘CYTOC’.

A log rank test stratified by stratification factor of PSADT ( $\leq 6$  vs.  $> 6$  months) and use of osteoclast-targeted therapy (yes vs. no) at randomization will be used to compare the darolutamide treated and placebo groups.

The hazard ratio as well as its 95% CI will be presented based on fitting a Cox regression model with treatment as factor and stratified by PSADT ( $\leq 6$  vs.  $> 6$  months) and use of osteoclast-targeted therapy (yes vs. no) at randomization.

Kaplan-Meier survival curves (product-limit estimates) will be presented by treatment arm. The Kaplan-Meier estimate of the median survival time and first and third quartiles will be presented with 95% CI. Greenwood's formula will be used for the standard error of the Kaplan-Meier estimate in the calculation of these confidence limits.

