 - ¹³ Blood (plasma) sampling for tumour-related biomarker evaluation will be collected on day 1 visit before study treatment administration, at the start of open-label treatment visit, and at the end-of-study treatment visit unless precluded by local guidelines, e.g. IEC/IRB or regulatory authorities. For placebo patients crossing over to open-label darolutamide treatment, sampling will not be performed at the end-of-study treatment visit (see [Table 4](#)).
 - ¹⁴ The local PSA result taken at screening should be used to confirm the patient has CRPC (inclusion criterion 4) and meets inclusion criterion 6.
 - ¹⁵ Only study drug accountability performed at the end-of-study treatment visit.
 - ¹⁶ A blood sample for DNA extraction will be taken at day 1 visit (or later during the study if feasible) only from patients who have signed the PG IC unless precluded by local guidelines, e.g. IEC/IRB or regulatory authorities.
 - ¹⁷ 12-lead ECG will be performed only at the start of open-label visit. ECG is not required on subsequent visits during the open-label darolutamide treatment.
 - ¹⁸ Survival data will also be collected through an additional survival sweep. All patients considered alive shortly after the database cut-off date for the MFS analysis and prior to any subsequent analysis of OS will be contacted for survival status.

Table 4. Study event schedule after withdrawal of study treatment or during the follow-up period; and study event schedule for placebo patients crossing over to open-label darolutamide treatment

Protocol activities	For patients discontinuing study drug before confirmed metastasis and not initiating any prohibited treatment *	For patients after confirmed metastasis, or receiving subsequent treatment after unblinding *	For placebo patients crossing over to open-label darolutamide	
	Visits Every 16 weeks (±7 days) from end-of-study treatment visit ¹	Visits or phone contacts Every 16 weeks (±7 days) from end-of- study treatment visit ²	Visits Every 16 weeks (±7 days) from start of open-label treatment visit ¹	End-of-study treatment visit 28 days (+7 days) after last dose or in transition to roll-over study
BPI-SF	X	X	X	X
Dispensing of pain diary	X	X	X	X
Collection of pain diary and pain medications	X ³	X ³	X ³	X
PCS subscale of FACT-P	X	X	X	X
ECOG performance status	X	X	X	X
Use of subsequent antineoplastic therapies	X	X	X	X
Laboratory safety assessments			X	X

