6.3.3.3 Time to initiation of subsequent antineoplastic therapy

Time to initiation of subsequent antineoplastic therapy is defined as time from randomisation to initiation of first antineoplastic therapy.

Subsequent antineoplastic therapy will be assessed from the first follow-up visit until the first use of such therapy.

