**Table 16: Censoring Rules for antineoplastic therapy**

Situation	End Date on or prior to cut-off date	Censored
Recorded antineoplastic therapy during the study	Date of the first assessment that qualified as antineoplastic therapy	No
Death during the study before antineoplastic therapy	Date of last visit at which antineoplastic therapy question was collected or randomization date whatever comes later	Yes
Patient has no recorded antineoplastic therapy at data cut-off	Date of last visit at which antineoplastic therapy question was collected or randomization date whatever comes later	Yes
Patient lost to follow-up before data cut-off	Date of last visit at which antineoplastic therapy question was collected or at the data cut-off, whichever occurs first	Yes

This endpoint is selected from the ADTTE dataset using variable PARAMCD equal to 'ISAT'.

A log rank test stratified by same stratification factors used in the MFS analysis will be used to compare the darolutamide treated and placebo groups.

The hazard ratio as well as its 95% CI will be generated with a Cox regression model as for MFS.

Kaplan-Meier survival curves (product-limit estimates) will be presented by treatment arm. The Kaplan-Meier estimate of the median time to initiation of subsequent antineoplastic therapy and first and third quartiles will be presented with 95% CIs.

A summary of first subsequent antineoplastic therapy will be provided.

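### SAP 6.2.2.3 gives two censoring rules for time to first chemotherapy; the operative Table 11, combined with the printed visit schedules, would censor men on double-blind treatment at randomisation

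*SAP*

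**What the plan says.** SAP v4.2, section 6.2.2.3, states two rules for a man who has had no chemotherapy. The text says: "Patients who have not taken cytotoxic chemotherapy will be right censored at their last visit". It then makes a table operative: "Table 11 will be used for calculating the time to first cytotoxic chemotherapy". All three censoring rows of Table 11 (death, no chemotherapy by cut-off, lost to follow-up) give the end date as "Date of last visit at which cytotoxic chemotherapy question was collected or randomization date whatever comes later". The note under the table says which question is meant: the CRF item "Has the patient taken any new antineoplastic therapy since previous visit" is taken to be enough because it "implies the question for cytotoxic chemotherapy".

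The schedule row that matches this item, "Use of subsequent antineoplastic therapies", stands in protocol Table 4 and in the follow-up schedule of SAP appendix 9.1. Protocol 6.1.3 lists the same item for follow-up contacts. The row is not in protocol Table 3, not in the on-treatment schedule of SAP appendix 9.1, and not in the visit lists of protocol 6.1.2.2 to 6.1.2.6. In protocol Table 4 it is also marked in both columns for placebo men crossing over to open-label darolutamide, so that group is asked while on drug. Darolutamide men who continue open-label follow Table 3, which lacks it.

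SAP Table 16, for subsequent antineoplastic therapy, uses "Date of last visit at which antineoplastic therapy question was collected or randomization date whatever comes later" in its death and cut-off rows. Its lost-to-follow-up row differs: it takes the earlier of the question visit and the data cut-off.

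**The concern.** The two rules in 6.2.2.3 can produce different datasets from the same CRF. Events come from the concomitant-medication dataset (SAP 9.7), so chemotherapy given at any time counts. Under Table 11, however, event-free time counts only up to a visit at which one particular question was asked. If that question is not asked on treatment, a man known to be free of chemotherapy after years on study drug adds no time at risk.

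The loss would not be balanced. Men leave study drug mainly through metastasis. If darolutamide delays metastasis, more darolutamide men are still on drug at cut-off, and more event-free time disappears from that arm. The men who remain are largely those who have already stopped drug, and among them the advantage from delayed metastasis has mostly been conditioned away.

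The endpoint carries alpha. It is third in the hierarchy of SAP 6.2.2, after overall survival and pain progression, and symptomatic skeletal events are tested only if it succeeds.

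**Working it through.** **Step 1: one man under each rule.** Take a man randomised 24 months before cut-off, still on double-blind drug, with no chemotherapy. With the SAP's 30.44 days per month this is 24 x 30.44 = 731 days. Visits every 16 weeks fall every 112 days; 731/112 = 6.5, so his last is the sixth, at day 6 x 112 = 672. The SAP time is end date minus randomisation date plus 1.
- Text of 6.2.2.3: 672 + 1 = 673 days, censored.
- Table 11, question asked only where the schedules print it: there is no question visit, so randomisation applies, giving 0 + 1 = 1 day, censored.

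**Step 2: the same wording elsewhere.** Tables 12 (SSE) and 15 (invasive procedures) also censor at the last assessment of the item. Both items have a row in protocol Table 3 from visit 2 onwards, so men on drug keep their time there. Tables 11 and 16 rely on an item without such a row.

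**Step 3: anchor to the plan's design.** The plan gives no design figure for this endpoint, so the MFS design was checked as the basis for a simulation. With 5% of 1500 = 75 uninformative baseline events among 385, the diluted hazard ratio is exp(ln 0.65 x 310/385) = 0.707, against the stated 0.71. Schoenfeld power is Phi(sqrt(385 x 1/3 x 2/3) x |ln 0.707| - 1.96) = Phi(9.25 x 0.347 - 1.96) = 89.4%, against about 91% by the plan's own simulation. That is close enough to use these inputs.

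**Step 4: size, by simulation.** From the documents: 1500 men, 2:1, 40 months' accrual, placebo MFS median 25 months, hazard ratio 0.65, cut-off at the 385th MFS event, 16-week visits, end-of-study treatment visit at 28 days. Assumed: exponential times; drug stopped at metastasis; chemotherapy only after metastasis, at a median of 12, 24 or 48 months later in both arms; either no dropout, or 40% by 36 months with those men lost. There were 400 runs per row. HR is the Cox hazard ratio for chemotherapy; power is nominal at z = 1.96.

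| Months, metastasis to chemotherapy | Dropout | Censored at randomisation under Table 11, darolutamide / placebo | HR, last visit | HR, Table 11 literal | Power, last visit / literal |
|---|---|---|---|---|---|
| 12 | none | 79.3% / 71.0% | 0.671 | 0.953 | 72.8% / 5.8% |
| 24 | none | 79.7% / 71.3% | 0.684 | 0.969 | 51.5% / 4.0% |
| 48 | none | 79.8% / 71.6% | 0.698 | 0.972 | 29.5% / 5.2% |
| 12 | 40% | 80.3% / 72.3% | 0.687 | 0.966 | 72.0% / 4.5% |
| 24 | 40% | 80.6% / 72.7% | 0.704 | 0.982 | 50.0% / 4.2% |
| 48 | 40% | 80.7% / 73.0% | 0.718 | 0.985 | 30.8% / 3.5% |

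The share censored at randomisation includes men who have stopped drug but not reached a first follow-up visit and, in the dropout rows, men lost before metastasis. The simulated cut-off fell at about 35 to 38 months, before accrual would end.

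**Step 5: different assumptions.** With cut-off fixed at 48 months, placebo median time to stopping drug 15-25 months and median time from stopping to chemotherapy 12-48 months (30 runs per setting), 52-67% of darolutamide and 38-55% of placebo men are censored at randomisation. The hazard ratio moves from 0.68-0.75 to 0.90-1.01.

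**Step 6: the final analysis.** Under protocol Table 4, crossover placebo men would regain event-free time up to their latest open-label visit. Darolutamide men continuing under Table 3 would stay at randomisation. The rule would then treat the arms differently by construction. This was not simulated.

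**The case against.** The strongest reply is that the documents do not show the question to be missing on treatment. Neither document contains the CRF or its visit map, and a schedule row lists an activity, not a CRF item. Protocol 6.3.2.3 has chemotherapy use assessed from randomisation. Protocol 5.7.1 records all concomitant treatments from consent to the end-of-study treatment visit, and Table 3 marks them at every visit. The Amendment 1 summary (Modification 12) explains that the separate chemotherapy item was dropped as redundant for that reason. Where the SAP clearly wants censoring at randomisation for missing assessments, as in Tables 10 and 17, it gives explicit rows; Table 11 has none for men on treatment. All this suggests that the intended rule is the one in the text.

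Much of that stands, and it limits what can be claimed:
- A reader might infer that men on study drug are in fact censored at randomisation. The documents do not support that; it needs both a literal derivation and a CRF that follows the printed schedules.
- A reader might infer that the question is asked only after treatment. Protocol Table 4 shows otherwise for crossover placebo men.
- A reader might take "Subsequent antineoplastic therapy will be assessed from the first follow-up visit until the first use of such therapy" (protocol 6.3.3.3) as confirmation. That sentence governs a different endpoint.

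The reply does not remove the conflict. Concomitant-treatment recording means that chemotherapy status is known on treatment, but Table 11 does not count that recording as a question visit, and 6.2.2.3 makes Table 11 the rule to follow.

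**Conclusion.** The concern holds in conditional form. SAP 6.2.2.3 contradicts itself, and its operative table relies on an item that the printed on-treatment schedules do not contain. Followed literally with a CRF that matches those schedules, it would censor at randomisation the men on double-blind treatment and the darolutamide men continuing open-label.

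The bias was towards a hazard ratio of 1 in all six scenarios of the main simulation, and the second set of assumptions agrees. Its size is illustrative: from about 0.7 to about 0.9-1.0. The documents give no treatment-stopping or chemotherapy rates, and the two simulations disagree on the share censored at randomisation (79-81% against 52-67% for darolutamide). The later cut-off and faster stopping in the second are consistent with its lower share. The powers compare the two rules only; the SAP's interim boundary is stricter than 1.96.

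A reader might infer a risk of a false claim of benefit. The simulations do not point that way: the error works against darolutamide, and the stakes are a distorted estimate and lost power on an endpoint that gates another.

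**What to change.** State one rule. In the three censoring rows of Table 11, censor at the last visit at which concomitant treatments were assessed (on treatment, through the end-of-study treatment visit) or subsequent antineoplastic therapy was assessed (follow-up), whichever is later. Use the randomisation date only for men with no post-randomisation visit. This agrees with the text of 6.2.2.3 and with protocol 6.3.2.3.

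Make the same change in the death and cut-off rows of Table 16. Reword its lost-to-follow-up row as well: it has no randomisation fallback, so it gives no clear date for a man with no question visit. The p-values for that endpoint are informative only, so this part is less pressing.

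Before programming, check the CRF visit map to see which forms carry the question. If it is already on the treatment-period forms, the numerical effect largely disappears, but the wording should still be aligned.

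The cost is SAP wording and one derivation for each endpoint. No new data are needed, because concomitant treatments are already collected at every Table 3 visit.
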